### 4.2.3 Rationale for Endpoints

#### 4.2.3.1 Efficacy Endpoints

**Primary Endpoint:** Overall response rate (ORR) at each treatment cycle 1 – 35 (each cycle is 3 weeks) based on RECIST 1.1. It is commonly used in clinical trials to evaluate cancer treatments for objective response in solid tumours. The observed effect is attributable directly to the drug, not the natural history of the disease. Its application in tumour progression measurement is well accepted by regulatory authorities.

**Secondary Endpoint:** Disease control rate (DCR, i.e. complete response (CR), partial response (PR) or stable disease (SD)) at 6, 12 and 24 months based on RECIST 1.1. For subjects who demonstrate CR, PR or SD, duration of response (DOR) is defined as the time from the start of study medication until the first sign of disease progression.

Progression Free Survival (PFS) measures the time from start of study medication until the first sign of disease progression based on RECIST 1.1 or death from any cause, whichever occurs first. It is a widely accepted endpoint in breast cancer Phase II clinical trials.

Overall Survival (OS) measures the date from study commencement to the date death from any cause. Patients alive or lost to follow up are censored. Overall survival as an endpoint is easily measured, unambiguous, objective and unaffected by the timing of assessment.

#### 4.2.3.2 Biomarker Research

**Planned Biomarker Research:** The specimens collected during clinical trial will be analysed to further investigate the association of genetic variants to the pembrolizumab, the molecular signatures correlate to the response of pembrolizumab and other biomarkers potentially be prognostic indicators to the response of pembrolizumab:

- Germline analyses (blood) which include single nucleotide polymorphism, whole exome sequencing or whole genome sequencing.
- Genetic analyses (tumour biopsy) which include Genome wide and targeted mutational analysis, mRNA expression and microRNA analysis may be performed.

- Other biomarkers: Tumour infiltrating lymphocytes (TILs) have been shown to provide prognostic and potentially predictive value. Hematoxylin and eosin-stained breast tumour sections will be evaluated for TILs, according to published and standardised methodology.

**Future Biomedical Research:** The specimens collected during clinical trial and not analysed will be stored and used for future biomedical research. This research may include genetic analyses DNA, RNA, metabolomics (serum/plasma) and/or the measurement of other analyses. Such research is for biomarker testing to address emergent not described elsewhere in the protocol (as part of the main trial) and will only be conducted on specimens collected from appropriately consented subjects within this study.

## 5.0 METHODOLOGY

### 5.1 Study Population

Written informed consent must be obtained before any study specific procedures are performed. Subjects must meet all the inclusion/exclusion criteria listed below.

#### 5.1.1 Inclusion Criteria

As this is a small Phase II study, only female patients will be included in order to reduce heterogeneity. Participants are eligible to be included in the study only if all of the following criteria apply:

1. Female participants who are at least 18 years of age on the day of signing informed consent with histologically confirmed HER2-negative breast cancer (infiltrating ductal or lobular breast carcinoma) with measurable metastatic disease.
2. Must have received at least one but not more than three (3) prior lines of palliative chemotherapy for metastatic breast cancer.
3. Have received at least one line of hormonal therapy in the metastatic setting, for patients with ER+ (positive) breast cancer.
4. Documented germline *APOBEC3B* mutation (i.e. germline deletion).
5. Can provide archival tumour tissue sample or willing to provide tissues from a newly obtained core or excisional biopsy of a tumour lesion not previously irradiated. Note: Formalin-fixed, paraffin embedded (FFPE) tissue blocks or slides allowed (10 unstained slides are needed);
6. Have measurable disease based on RECIST 1.1 as determined by local radiology review. Lesions situated in a previously irradiated area are considered measurable if progression has been demonstrated in such lesions.
7. Have Eastern Cooperative Oncology Group (ECOG) performance status of 0 or 1 (assessed within 10 days prior to the start of study treatment).
8. Have life expectancy of at least 3 months.
9. Have adequate organ function, within 10 days prior to the start of study treatment, as defined in the following:
  - a. Absolute neutrophil count (ANC)  $\geq 1,500/\mu\text{l}$ .
  - b. Hemoglobin (Hb)  $\geq 9$  g/dL or 5.6mmol/La.
  - c. Platelets  $> 100,000/\mu\text{l}$ .
  - d. Creatinine  $\leq 1.5$  times ULN.
  - e. ALT (SGPT) and AST (SGOT)  $\leq 2.5$  times the ULN ( $\leq 5$  times for patients with liver metastases).
  - f. Total bilirubin  $\leq 1.5$  mg/dL.
10. LDH  $\leq 2.0$  times the ULN. Women of child-bearing potential must have a negative urine or serum pregnancy test within 72 hours prior to receiving the first dose of study treatment.

11. Women of child-bearing potential prepared to use adequate contraceptive measures if sexually active for the course of the study through 120 days after the last dose of treatment.
12. Have signed informed consent and able to comply with scheduled visits, treatment plan and other study procedures.

### 5.1.2 Exclusion Criteria

Participant is excluded from the study if any of the following criteria apply:

1. Has HER2-positive breast cancer (FISH/CISH confirmed status, or 3+ IHC status)
2. Has use of any investigational agent or participation in another therapeutic clinical trial concurrently or in the 30 days prior to inclusion.
3. Has not recovered (e.g. to  $\leq$ Grade 1 or to baseline) from AEs due to a previously administered therapy. Note: Participants with  $\leq$ Grade 2 neuropathy may be eligible.
4. Has an active autoimmune disease that has required systemic treatment in the past 2 years (e.g. with the use of disease modifying agents, corticosteroids or immunosuppressive drugs). Replacement therapy (e.g., thyroxine, insulin or physiologic corticosteroid replacement therapy for adrenal or pituitary insufficiency) is not considered a form of systematic treatment.
5. Has a diagnosis of immunodeficiency or is receiving systematic steroid therapy or any other form of immunosuppressive therapy within 7 days prior to study treatment.
6. Has a concurrently active second malignancy, other than adequately treated non-melanoma skin cancers, in situ melanoma or in situ cervical cancer. Subjects with other non-mammary malignancies must have been disease-free for at least 5 years.
7. Has known active CNS metastases and/or carcinomatous meningitis. Previously treated brain metastases may participate provided these remain stable.
8. Has received prior therapy with an anti-PD1, anti-PDL1 or anti-PDL2 agent or with an agent directed to another co-inhibitory T cell receptor (such as CTLA-4, OX-40, and CD137) or has previously participated in pembrolizumab clinical studies.
9. Patient who has received a live vaccine within 30 days of the first dose of study drug.
10. Known hypersensitive or allergy to pembrolizumab and any of its components.
11. Patient who is pregnant or breastfeeding.
12. Patient with an expected life expectancy of less than 3 months.
13. History of significant comorbidities that, in the opinion of the investigator, may interfere with the conduct of the study, the evaluation of response, or with informed consent.
14. Active uncontrolled infection at the time of inclusion.
15. Has a history of class II-IV congestive heart failure or myocardial infraction.
16. Has known psychiatric or substance abuse disorders that would interfere with cooperation with the requirements of this study
17. Has evidence of active pneumonitis, or non-infectious pneumonitis requiring treatment with steroids.
18. Has a known history of Human Immunodeficiency Virus (HIV).
19. Has a known history of Hepatitis B (defined as Hepatitis B surface antigen [HBsAg] reactive) or known active Hepatitis C virus (defined as HCV RNA [qualitative] is detected) infection. Note: no testing for Hepatitis B and Hepatitis C is required unless mandated by local health authority.

### 5.1.3 Lifestyle Restrictions

#### 5.1.3.1 Meals and Dietary Restrictions

Participants should maintain a normal diet unless modifications are required to manage an AE such as diarrhea, nausea or vomiting.

#### 5.1.3.2 Contraception

Pembrolizumab may have adverse effects on a fetus in utero. Refer to Appendix 3 for approved methods of contraception.

### 5.1.4 Pregnancy

If a participant inadvertently becomes pregnant while on treatment with pembrolizumab, the participant will be immediately discontinued from study treatment. The site will contact the participant at least monthly and document the participant's status until the pregnancy has been completed or terminated. The outcome of the pregnancy will be reported to Merck within 2 working days if the outcome is a serious adverse experience (eg, death, abortion, congenital anomaly, or other disabling or life-threatening complication to the mother or newborn). The study Investigator will make every effort to obtain permission to follow the outcome of the pregnancy and report the condition of the fetus or newborn to Merck.

### 5.1.5 Use in Nursing Women

It is unknown whether pembrolizumab is excreted in human milk. Since many drugs are excreted in human milk, and because of the potential for serious adverse reactions in the nursing infant, participants who are breast-feeding are not eligible for enrollment.

## 5.2 Trial Treatments

The treatment to be used in this trial is outlined below in Table 1.

**Table 1 Trial Treatment**

Drug	Dose/ Potency	Dose Frequency	Route of Administration	Regimen/ Treatment Period	Use
Pembrolizumab	200 mg	Q3W	IV infusion	Day 1 of each 3 week cycle	Experimental

Trial treatment should begin on the day of treatment allocation or within 3 days of treatment allocation.

#### 5.2.1 Timing of Dose Administration

Trial treatment should be administered on Day 1 of each cycle after all procedures/assessments have been completed as detailed on the Trial Flow Chart (Section 6.0). Trial treatment may be administered up to 3 days before or after the scheduled Day 1 of each cycle due to administrative reasons.

All trial treatments will be administered on an outpatient basis.

Pembrolizumab 200 mg will be administered as a 30 minute IV infusion every 3 weeks. Sites should make every effort to target infusion timing to be as close to 30 minutes as possible. However, given the variability of infusion pumps from site to site, a window of -5 minutes and +10 minutes is permitted (i.e., infusion time is 30 minutes: -5 min/+10 min).

The Pharmacy Manual contains specific instructions for the preparation of the pembrolizumab infusion fluid and administration of infusion solution.

### **5.2.2 Dose Modification and toxicity management for immune-related AEs associated with pembrolizumab**

AEs associated with pembrolizumab exposure may represent an immunologic etiology. These immune-related AEs (irAEs) may occur shortly after the first dose or several months after the last dose of pembrolizumab treatment and may affect more than one body system simultaneously. Therefore, early recognition and initiation of treatment is critical to reduce complications. Based on existing clinical study data, most irAEs were reversible and could be managed with interruptions of pembrolizumab, administration of corticosteroids and/or other supportive care. For suspected irAEs, ensure adequate evaluation to confirm etiology or exclude other causes. Additional procedures or tests such as bronchoscopy, endoscopy, skin biopsy may be included as part of the evaluation. Based on the severity of irAEs, withhold or permanently discontinue pembrolizumab and administer corticosteroids. Dose modification and toxicity management guidelines for irAEs associated with pembrolizumab are provided in Table 2).

**Table 2 Dose modification and toxicity management guidelines for immune-related AEs associated with pembrolizumab**

General instructions:				

 
1. Corticosteroid taper should be initiated upon AE improving to Grade 1 or less and continue to taper over at least 4 weeks.
 
2. For situations where pembrolizumab has been withheld, pembrolizumab can be resumed after AE has been reduced to Grade 1 or 0 and corticosteroid has been tapered. Pembrolizumab should be permanently discontinued if AE does not resolve within 12 weeks of last dose or corticosteroids cannot be reduced to <math>\leq 10</math> mg prednisone or equivalent per day within 12 weeks.
 
3. For severe and life-threatening irAEs, IV corticosteroid should be initiated first followed by oral steroid. Other immunosuppressive treatment should be initiated if irAEs cannot be controlled by corticosteroids.
 
				
Immune-related AEs	Toxicity grade or conditions (CTCAEv4.0)	Action taken to pembrolizumab	irAE management with corticosteroid and/or other therapies	Monitor and follow-up
Pneumonitis	Grade 2	Withhold	
 
• Administer corticosteroids (initial dose of 1-2 mg/kg prednisone or equivalent) followed by taper
 
	
 
• Monitor participants for signs and symptoms of pneumonitis
 
• Evaluate participants with suspected pneumonitis with radiographic imaging and initiate corticosteroid treatment
 
• Add prophylactic antibiotics for opportunistic infections
 

	Grade 3 or 4, or recurrent Grade 2	Permanently discontinue		
Diarrhea / Colitis	Grade 2 or 3	Withhold	
 
• Administer corticosteroids (initial dose of 1-2 mg/kg prednisone or equivalent) followed by taper
 
	
 
• Monitor participants for signs and symptoms of enterocolitis (ie, diarrhea, abdominal pain, blood or mucus in stool with or without fever) and of bowel
 

	Grade 4	Permanently discontinue		
perforation (ie, peritoneal signs and ileus).
 
 
• Participants with <math>\geq</math> Grade 2 diarrhea suspecting colitis should consider GI consultation and performing endoscopy to rule out colitis.
 
• Participants with diarrhea/colitis should be advised to drink liberal quantities of clear fluids. If sufficient oral fluid intake is not feasible, fluid and electrolytes should be substituted via IV infusion.
 

AST / ALT elevation or Increased bilirubin	Grade 2	Withhold	
 
• Administer corticosteroids (initial dose of 0.5- 1 mg/kg prednisone or equivalent) followed by taper
 
	
 
• Monitor with liver function tests (consider weekly or more frequently until liver enzyme value returned to baseline or is stable)
 

	Grade 3 or 4	Permanently discontinue	
 
• Administer corticosteroids (initial dose of 1-2 mg/kg prednisone or equivalent) followed by taper
 
	
Type 1 diabetes mellitus (T1DM) or Hyperglycemia	Newly onset T1DM or Grade 3 or 4 hyperglycemia associated with evidence of $\beta$ -cell failure	Withhold	
 
• Initiate insulin replacement therapy for participants with T1DM
 
• Administer anti-hyperglycemic in participants with hyperglycemia
 
	
 
• Monitor participants for hyperglycemia or other signs and symptoms of diabetes.
 

Hypophysitis	Grade 2	Withhold	
 
• Administer corticosteroids and initiate hormonal replacements as clinically indicated.
 
	
 
• Monitor for signs and symptoms of hypophysitis (including hypopituitarism and adrenal insufficiency)
 

	Grade 3 or 4	Withhold or permanently discontinue 		

Hyperthyroidism	Grade 2	Continue	
 
Treat with non-selective beta-blockers (eg, propranolol) or thionamides as appropriate
 
	
 
Monitor for signs and symptoms of thyroid disorders.
 

	Grade 3 or 4	Withhold or permanently discontinue 		
Hypothyroidism	Grade 2-4	Continue	
 
Initiate thyroid replacement hormones (eg, levothyroxine or liothyronine) per standard of care
 
	
 
Monitor for signs and symptoms of thyroid disorders.
 

Nephritis and Renal dysfunction	Grade 2	Withhold	
 
Administer corticosteroids (prednisone 1-2 mg/kg or equivalent) followed by taper.
 
	
 
Monitor changes of renal function
 

	Grade 3 or 4	Permanently discontinue		
Myocarditis	Grade 1 or 2	Withhold	
 
Based on severity of AE administer corticosteroids
 
	
 
Ensure adequate evaluation to confirm etiology and/or exclude other causes
 

	Grade 3 or 4	Permanently discontinue		
All other immune-related AEs	Intolerable/persistent Grade 2	Withhold	
 
Based on type and severity of AE administer corticosteroids
 
	
 
Ensure adequate evaluation to confirm etiology and/or exclude other causes
 

	Grade 3	Withhold or discontinue based on the type of event. Events that require discontinuation include and not limited to: Guillain-Barre Syndrome, encephalitis		

	Grade 4 or recurrent Grade 3	Permanently discontinue		

1. Withhold or permanently discontinue pembrolizumab is at the discretion of the investigator or treating physician.
 
NOTE:                      For participants with Grade 3 or 4 immune-related endocrinopathy where withhold of pembrolizumab is required, pembrolizumab may be resumed when AE resolves to <math>\leq</math> Grade 2 and is controlled with hormonal replacement therapy or achieved metabolic control (in case of T1DM).
				

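### Protocol Table 2 has two restart rules that do not fit together for hypophysitis: a Grade 2 event meets a stricter restart condition than a withheld Grade 3 or 4 event now in the same state.

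*Protocol*

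**What the plan says.** Everything at issue is in Protocol Section 5.2.2, Table 2.

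- **General instruction 2, scope and restart condition.** It opens with "For situations where pembrolizumab has been withheld" and names no exception. The restart condition is "pembrolizumab can be resumed after AE has been reduced to Grade 1 or 0 and corticosteroid has been tapered".
- **General instruction 2, stopping clause.** "Pembrolizumab should be permanently discontinued if AE does not resolve within 12 weeks of last dose or corticosteroids cannot be reduced to" 10 mg or less of prednisone (or equivalent) a day within 12 weeks.
- **General instruction 1.** "Corticosteroid taper should be initiated upon AE improving to Grade 1 or less and continue to taper over at least 4 weeks".
- **Hypophysitis rows.** Grade 2 is withheld. Grade 3 or 4 is either withheld or permanently discontinued, and footnote 1 leaves that choice to the physician. The management column says "Administer corticosteroids and initiate hormonal replacements as clinically indicated".
- **NOTE under the table.** "For participants with Grade 3 or 4 immune-related endocrinopathy where withhold of pembrolizumab is required, pembrolizumab may be resumed when AE resolves to" Grade 2 or lower and is controlled on hormone replacement, or metabolically controlled for type 1 diabetes.
- **Myocarditis row.** "Myocarditis Grade 1 or 2 Withhold", with the steroid column reading "Based on severity of AE administer corticosteroids".

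**The concern.** The two restart rules use different grade thresholds, and which one applies depends on how severe the event was at the start, not on the patient's present state. For hypophysitis the order comes out reversed: the event that never passed Grade 2 has the harder restart condition.

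Table 2 is an operative instruction. Section 5.3.3 sends sites to it for dose modification, and Section 5.4 requires discontinuation for unacceptable adverse experiences as described in Section 5.2.2. Sites that follow the wording literally would give opposite instructions to two patients in the same condition. Sites that notice the problem may resolve it in different ways. What is at stake is consistent handling of re-dosing and of permanent loss of study drug in individual patients, more than any design quantity.

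The myocarditis row raises a smaller question: what must change before a Grade 1 event, withheld at Grade 1, satisfies a rule whose resume range already includes Grade 1?

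**Working it through.** The plan gives no figure to reproduce and no sample-size arithmetic applies. The check takes each Table 2 entry that can lead to a withhold, finds the restart rule that governs it, and compares the grade that triggers the withhold with the grade at which restart is allowed.

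| Event | Grade withheld | Governing rule | Restart grade | Result |
|---|---|---|---|---|
| Pneumonitis | 2 | Instruction 2 | 0–1 | No overlap |
| Diarrhea/colitis | 2–3 | Instruction 2 | 0–1 | No overlap |
| AST/ALT or bilirubin | 2 | Instruction 2 | 0–1 | No overlap |
| Nephritis | 2 | Instruction 2 | 0–1 | No overlap |
| Other immune-related | 2, and 3 where withheld | Instruction 2 | 0–1 | No overlap |
| Hyperthyroidism | 3–4 where withheld | NOTE | 2 or lower, controlled | Coherent: Grade 2 continues treatment |
| Hyperglycemia with β-cell failure | 3–4 | NOTE | 2 or lower, metabolic control | No overlap |
| New-onset type 1 diabetes | no grade given | NOTE names the condition | – | Cannot be compared |
| **Hypophysitis** | **2** | **Instruction 2** | **0–1, steroid tapered** | **Stricter** |
| **Hypophysitis** | **3–4 where withheld** | **NOTE** | **2 or lower, controlled** | **Less strict on grade** |
| **Myocarditis** | **1–2** | **Instruction 2** | **0–1** | **Overlap at Grade 1** |

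Hypothyroidism does not enter the table because Grades 2 to 4 continue treatment.

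**Hypophysitis, two patients side by side.** Both are now at Grade 2 and controlled on hormone replacement.

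1. Patient A never exceeded Grade 2. The NOTE does not reach her, so instruction 2 applies. She is not at Grade 1 or 0, so the grade condition fails. If steroid was given, instruction 1 starts the taper only at Grade 1 or less, so the taper condition fails as well. If she stays at Grade 2, the 12-week clause points to permanent discontinuation. On three-week cycles that is 12 / 3 = 4 dosing intervals after her last dose.
2. Patient B reached Grade 3 or 4 and was withheld rather than discontinued. The NOTE applies, and she meets both of its conditions. She may restart.

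The state is the same and the instructions are opposite. Hypophysitis is the only endocrine row that withholds at a grade where the NOTE permits dosing. The NOTE repeats neither the taper condition nor the 12-week clause, and it waives neither. Whether those parts of instruction 2 bind an endocrine event controlled on replacement is therefore not stated.

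**Myocarditis.** Grade 1 is both a withhold grade and a resume grade. An event that begins at Grade 1 cannot be reduced to Grade 1, so the clause is either met at onset or has no clear meaning until Grade 0. If steroid is given, the taper of at least four weeks still delays restart. The row makes steroid depend on severity, so a Grade 1 case might receive none. The text does not say whether an absent taper counts as a completed one.

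**Trial figures.** No restart rule enters the Simon design in Section 8.4 (22, then 18, for 40 evaluable, 44 enrolled). The Full Analysis Set in Section 8.5 requires one dose and a baseline scan with measurable disease, so a patient stopped early stays in the denominator. One patient among 40 evaluable is 1/40 = 2.5 percentage points of response rate. That would move only if the stop cost a response that would otherwise have followed.

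**The case against.** The strongest reply is that the NOTE is a deliberate exception to a general rule and that Table 2 is guidance. Instruction 2 says that treatment can be resumed and should be stopped. It does not define resolution, and the NOTE itself speaks of an event resolving to Grade 2 or lower. Grade 3 or 4 hypophysitis may also end treatment, at the physician's choice. All of this is fair, and it limits how strongly the consequence can be put. It does not remove the reversal. An exception that relaxes the rule for the severe event but not the mild one gives a result that the table does not explain, and footnote 1's discretion does not extend to the Grade 2 row.

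A reader might infer three stronger points that the documents do not support.

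- *That the myocarditis withhold protects no one because re-dosing is allowed at once.* This needs two assumptions that the text does not make: that no steroid is given, and that an absent taper satisfies the taper condition. Section 5.2.2 pairs withholding with corticosteroids, the row asks for evaluation of etiology, and Section 5.4 requires discontinuation where the investigator or sponsor judges the risk unnecessary. The row is unclear, not contradictory.
- *That type 1 diabetes below Grade 3 is forced off treatment.* The row assigns no grade to new-onset type 1 diabetes, and the NOTE names the condition. The table contains no such category.
- *That mild hypophysitis always ends treatment and severe hypophysitis never does.* The Grade 3 or 4 cell allows permanent discontinuation, and the NOTE does not expressly lift the 12-week clause.

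**Conclusion.** The point holds for hypophysitis. Read literally, the Grade 2 row under instruction 2 and the NOTE for Grade 3 or 4 give opposite instructions to two patients in the same controlled Grade 2 state, and the milder history meets the stricter rule. The reach of the 12-week clause over endocrine events controlled on replacement is also unstated. Grade 1 myocarditis is a secondary matter of unclear wording.

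The conclusion rests on reading the NOTE as limited to the grades it names, and on the Grade 3 or 4 event having been withheld rather than discontinued. It takes no view on which restart condition is clinically right.

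The size in patients cannot be computed, because the documents give no incidence for either event. The Simon design figures are unaffected. On the assumption that few of the 44 patients are affected, the influence on the response rate is small. The case for acting is consistent handling of re-dosing, at little cost.

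**What to change.** The sponsor should reconcile three parts of Table 2 so that they agree: the Grade 2 hypophysitis row, general instruction 2 including its 12-week clause, and the NOTE. The revised text should make clear which restart rule governs each grade of hypophysitis that is withheld, and whether the 12-week and steroid-taper conditions apply to endocrine events controlled on replacement. It should also say how instruction 2 applies to myocarditis withheld at Grade 1, including when no corticosteroid was given. The clinical content and the form of each condition are for the sponsor to decide.

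The cost is a wording change to Table 2 in a protocol amendment and a notice to sites. It adds no visits or tests and needs no change to the sample size or analysis.
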